4.2.4 Randomisation

After screening for inclusion and non-inclusion criteria, and obtaining consent, patients will be randomized (1:1 ratio) to cilostazol or placebo groups by logging onto a randomization website using a pre-prepared randomization list, balanced by randomly variable block size. Randomization will be stratified by centre, age (<50 years; >=50 and <=75 Years; >75 years); and severity (Fisher grade from I to III; Fisher grade IV)

"CASH" protocol, version 2.1 of 04/04/2025

Randomisation will occur in an online data entry platform, guaranteeing the concealment of the experimental arm assigned to the doctor performing the inclusion and randomisation of the patient.

The randomisation code will be disclosed once recruitment is completed.

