10.3.7 Data Safety Monitoring Board

The Data and Safety Monitoring Board (DSMB) can be established by the sponsor. Its primary mission is to serve as a committee for monitoring safety data. It can have other missions, such as monitoring efficacy data (especially if the protocol includes interim analyses).

The DSMB is mentioned in Article L. 1123-7 of the French Public Health Code.

The sponsor is responsible for justifying the creation or absence of a supervisory committee to the Competent Authority (ANSM) and to the CPP.

A DSMB will be convened for this biomedical research. The members of the DSMB will be named after the research starts. During the first meeting of the DSMB, a chairman will be appointed and the members will determine their operating methods and the meeting schedule. All missions as well as the precise operating methods of the DSMB will be described in the DSMB's charter for the research.

General information about the DSMB

The DSMB makes recommendations to the sponsor about the continuation, modification or termination of the research upon interim analysis. The recommendations that the DSMB can make are:

- to continue the research with no modifications
- to continue the research with a modification to the protocol and/or to the monitoring of subjects
- to temporarily halt inclusions
- to permanently terminate the research in light of:
 - o safety data: serious adverse reactions
 - o efficacy data: proven futility or efficacy

The DSMB is appointed by the sponsor and is made up of at least 3 people with no connection to the research, including at least one clinician specialising in the pathology being studied and one specialist in the medication being studied (or a pharmacologist/pharmacovigilance specialist), and possibly a methodologist/biostatistician, particularly in the case of interim analysis.

The DSMB has a consultative role in advising the sponsor on safety issues such as tolerance and re-assessment of the benefit-risk ratio during the research.

The DSMB must hold its preliminary meeting before the first inclusions of the first subject and ideally before the protocol is submitted to the competent authority and the CPP. The committee's agenda will be as follows:

Definition of the DSMB's missions:

- Validation of the research methodology:

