The proposed methodology for the clinical trial will be validated by the DSMB so that it does not jeopardise the safety of subjects, in particular relating to the inclusion and randomization methods.

- Validation of tolerance monitoring methods:
 - o nature of the evaluated parameters
 - o frequency of the evaluations, consultation schedule
- Validation of termination criteria:
 - o criteria for terminating a subject's participation for tolerance reasons

- criteria for the temporary or permanent termination of the research (leading to the establishment of certain recommendations ("stopping rules"))
- Modification of the protocol and recommendations:
In light of the analysis of tolerance data for the research, the DSMB can, when applicable: propose substantial modifications in order to modify certain data, in particular relating to the protocol (inclusion and non-inclusion criteria, monitoring, additional exams, etc.). Likewise the DSMB can issue any recommendations it deems useful in order to best ensure the safety of the research subjects and to maintain a favourable benefit-risk balance throughout the research.

Definition of the DSMB's operating methods:

- meeting types (open session, then closed sessions) and schedule
- desired methods and format of SAE notification from the sponsor to the DSMB

The DSMB appoints its chairman at the first meeting.

The sponsor retains decision-making authority. When applicable, the sponsor delivers its decision, with justification, and DSMB reports to the Competent Authority (ANSM) and the CPP.

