In light of the results obtained for the sample size estimation, an OR between the two arms of 1.86 is assumed as a precaution. This assumption sets the proportion of patients who will obtain a favourable outcome in the control arm at 65% and the proportion of responders in the experimental arm at least 76%. These proportions may appear high, but it should be noted that the study does not include patients with early death and without surgery.

The experimental design includes two intermediate analyses; a sequential group test and the O'Brian-Fleming Analog spending function for alpha and beta errors were used.

Therefore set unilateral alpha at 0.025 and the power of the test (1-beta) at 0.80, 284 patients are needed per experimental arm; details are given in table 3 and figure 1.

A drop-out rate of no more than 10% is expected so that the sample size will be 630 patients (315 per experimental arm).

All estimates for the interim analyses are made without considering the inflation quota for drop-out patients. Therefore this evaluation will be made at the planned number of patients who completed the study. Only the final analysis will bear any inflationary share of the sample.

Table 3. Summary Report -

Item	Value
Maximum Number of Stages (Design):	3
Current Stage:	0
Alternative Hypothesis:	$P1 - P2 < 0$ (one-sided)
Alpha Spending Function:	O'Brien-Fleming Analog
Beta Spending Function:	O'Brien-Fleming Analog
Futility Boundaries:	Binding
Target Alpha:	0.025
Alpha (from simulations):	0.025
P1:	0.65
P2:	0.76
N1 (if final stage reached):	284
N2 (if final stage reached):	284
Target Power:	0.8
Power (from simulations):	0.8016
Maximum Information:	692.8

Information Report

Maximum Information: 692.8519

 Alternative Hypothesis: $P1 - P2 < 0$ (one-sided)

Alpha: 0.0250

Stage	Target information proportion	Target sample size N1	Target sample size N2	P1	P2
1	0.33	95	95	0.65	0.76
2	0.67	189	189	0.65	0.76
3	1.00	284	284	0.65	0.76

Alpha Spending

Target Final Stage Alpha: 0.0250

Spending Function: O'Brien-Fleming Analog

Stage	Information proportion	Alpha spent this stage	Cumulative alpha spent	Percentage alpha spent at this stage	Cumulative percentage
1	0.33	0.0001	0.0001	0.4	0.4
2	0.67	0.0059	0.0060	23.8	24.2
3	1.00	0.0190	0.0250	75.8	100.0

Beta Spending for Futility

Target Cumulative Beta at Final Stage: 0.2000

Spending Function for Futility: O'Brien-Fleming Analog

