Stage	Information proportion	Beta spent this stage	Cumulative beta spent	Percentage beta spent at this stage	Cumulative percentage
1	0.33	0.0264	0.0264	13.2	13.2
2	0.67	0.0901	0.1165	45.7	58.3
3	1.00	0.0835	0.2000	41.7	100.0

Boundary Probabilities for $\delta = -0.11$

Number of Simulations: 100000

Futility Boundaries: Binding

After Efficacy Boundary Crossing: Hold Out

After Binding Futility Boundary Crossing: Hold Out

 Alternative Hypothesis: $P1 - P2 < 0$ (one-sided)

P1: 0.65

P2: 0.76

 δ : -0.11

Stage	N1	N2	Efficacy		Futility	
			Boundary	Probability	Boundary	Probability
1	95	95	-3.7103	0.0253	0.2701	0.0277
2	189	189	-2.5111	0.4166	-1.1224	0.0885
3	284	284	-1.9308	0.3597	-1.9308	0.0821

Average N1: 226.

Average N2: 226

[figure not shown]

Figure 1.

12.6 Specify if subjects who leave the research prematurely will be replaced and in what proportion.

The primary outcome is assessed only one time 6 months after Day 0 (5 months and a half after last day of treatment) that could lead to patient's loss to follow up. Nevertheless, SAH is a serious condition that requires a long and close patient's monitoring. That will limit patient's loss to follow up. The patients who leave study prematurely (for loss to follow up or death) won't be replaced and will be considered as non responder patients in the main analysis of primary criterion.

Some sensitivity analyses will be performed with complete cases only.

Only, the particular circumstance of patient resignation will lead to exit patient of the primary analysis. A 10% rate of non evaluable patients is foreseen.

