1	0.556	315	315	0.025	0.65	0.73
2	0.656	315	315	0.025	0.65	0.74
2	0.753	315	315	0.025	0.65	0.75

Should one of the scenarios occur, a new sample size estimate will be possible. A conditional power analysis for the emerging z-value will be performed and provided to the IDMC.

Independent Data Monitoring Committee (IDMC)

An independent Data Monitoring Committee (IDMC) will closely review the safety data and efficacy of the interim analysis and provide recommendations for the continuation of the study. The IDMC will be composed of at least three members, of which at least one will be a specialist in the domain of neurology and at least one in the domain of reanimation and a methodologist. The members of the IDMC will be appointed before the protocol is submitted to the ethics committee for final approbation.

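### The final limit of -1.9308 holds one-sided alpha at 0.025 only if every futility crossing stops the trial, and the protocol's governance does not assure that stop

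*Protocol*

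**What the plan says.** Section 12.5 plans three looks at 95, 189 and 284 patients per arm, with O'Brien-Fleming-type spending for both alpha and beta, and "set unilateral alpha at 0.025 and the power of the test (1-beta) at 0.80". The output states "Futility Boundaries: Binding" and treats a trial that has crossed futility as unable to reject later. Efficacy limits are -3.7103, -2.5111 and -1.9308; interim futility limits are 0.2701 and -1.1224. Negative z favours cilostazol.

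Section 12.7 divides each interim result into three zones and labels one of them a stop for futility. It then passes the analysis to the monitoring committee for advice; that committee is to "provide recommendations for the continuation of the study". The futility limit at look 2 is printed there as -1.224.

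Section 10.3.7 says "The DSMB makes recommendations to the sponsor about the continuation, modification or termination of the research upon interim analysis". Continuing unchanged is among the recommendations open to the board, and "The sponsor retains decision-making authority". Section 5.8.4 words termination as something the sponsor or the authority can do on the board's recommendation, and lists futility among the situations.

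Section 12.5 also says that the interim looks ignore the drop-out allowance and that only the final analysis carries it, so the final look may have up to 315 per arm.

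**The concern.** After two earlier efficacy looks, a one-sided 0.025 test would normally need a final limit above 1.96. A final limit of 1.9308 is possible only because the calculation removes every trial that has crossed a futility limit. That credit is earned only if such trials really stop. If one continues and is tested at -1.9308, paths that the calculation counted as ended can still produce a rejection, and total alpha exceeds 0.025.

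Section 12.5 therefore assumes a compulsory stop, while the decision-making text leaves the stop to the sponsor's judgement. At stake is the type I error statement for the primary test. The situation would be common under the null: with the tabulated limits, futility is crossed first at look 1 with probability 0.3935 and at look 2 with probability 0.4795, about 87% of null trials in all.

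**Working it through.** **Inputs (section 12.5).** Response rates 0.65 and 0.76; looks at 95, 189 and 284 per arm; efficacy limits 3.7103, 2.5111, 1.9308; futility limits -0.2701 and 1.1224 (signs reversed so that positive favours cilostazol); one-sided alpha 0.025.

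**Method.** Recursive numerical integration of the joint normal distribution of the three z-statistics, with information fractions n_k/n_final. Under the alternative, the drift of the final z is 0.11 × √(n/v), with v = 0.65×0.35 + 0.76×0.24 = 0.4099.

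**1. Reproduce the protocol's figures.**
- Information: 284/0.4099 = 692.85 (stated 692.8519).
- Drift: 0.11 × √692.85 = 2.895.
- Alpha with futility obeyed: 0.0001 + 0.0059 + 0.0190 = 0.0250 (stated 0.025).
- Power: 0.8025 (stated 0.8016 by simulation).
- Solving for the final limit with binding futility gives 1.930 to 1.931 (stated 1.9308).

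The table is arithmetically sound under its own assumption.

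**2. Remove the compulsory stop, keep the efficacy limits, and evaluate under the null.**

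| Futility handling | Alpha, final 284 per arm | Alpha, final 315 per arm |
|---|---|---|
| Obeyed at both looks | 0.0250 | 0.0241 |
| Overridden at look 1 only | 0.0254 | 0.0245 |
| Overridden at look 2 only | 0.0277 | 0.0279 |
| Overridden at both looks | 0.0284 | 0.0289 |

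At 284 per arm nearly all the excess arises at the final look, where alpha spent rises from 0.01895 to 0.02237, a difference of 0.0034. A binomial simulation of 2,000,000 trials at 284 per arm with both looks overridden gave 0.0282 to 0.0292, depending on the null rate and on whether the variance was pooled.

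**3. Final limit that needs no futility credit.** Keep the first two efficacy limits and solve for the last one so that total alpha is 0.025 with futility ignored.
- 284 per arm: 1.993. Power with futility followed falls from 0.803 to 0.791.
- 315 per arm: 2.002. Power with futility followed falls from 0.824 to 0.813.

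The exposed range of final |z| after an override is therefore 1.931 to 1.993 at 284 per arm, and 1.931 to 2.002 at 315.

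**4. The two look-2 futility limits.** Obeying -1.224 (section 12.7) instead of -1.1224 (section 12.5 table) gives alpha 0.0241 at 284 per arm. This discrepancy does not inflate alpha, but it leaves the limit that is meant to bind uncertain.

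**The case against.** The strongest reply is that the protocol does state a rule. Section 12.5 declares the limits binding, and section 12.7 sets out exhaustive zones with a stop in the futility zone, without qualifying words. An advisory committee and a deciding sponsor are compatible with a binding limit if the sponsor has committed in advance to follow it. Part of section 10.3.7 is general wording about safety monitoring, and it leaves operating details to a charter that is not shown.

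Much of this stands. A reader might infer that the protocol contains no futility stopping rule; section 12.7 does not support that. A reader might also infer that the sample size table is wrong; it reproduces. What the reply does not supply is the advance commitment. Section 12.7 itself follows the zones with advice on continuation, and sections 5.8.4 and 10.3.7 leave the choice to the sponsor, with futility and interim analyses expressly in view.

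A second reply is that the inflation is small and conditional. That also stands. The value 0.0284 requires every crossing at both looks to be overridden. Overriding look 1 alone adds only 0.0004 at 284 per arm and stays below 0.025 at 315.

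**Conclusion.** The point holds as a conflict between a binding calculation and advisory governance. One-sided alpha of 0.025 at a final limit of -1.9308 is conditional on a stop that the protocol does not assure. The excess is modest: at most 0.0034 at 284 per arm (0.0284 against 0.025) and 0.0039 at 315 (0.0289), mainly from overriding look 2.

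It would be tempting to say that any positive final result after an overridden crossing is indefensible. The figures do not support that: a final |z| above about 1.993 (284 per arm) or 2.002 (315 per arm) still meets 0.025. Nor is alpha inflated if the trial is run as section 12.7 labels its zones.

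These results assume looks at the planned 95 and 189 per arm, the normal approximation, and no sample size change at look 2. The re-estimation that section 12.7 allows is not included. The point ranks as should-fix.

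**What to change.** Settle one of two routes before the first interim analysis.

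- **Non-binding futility.** Keep the futility limits as guidance and replace the final efficacy limit with about -1.993 (284 per arm) or about -2.002 (315 per arm). Restate power with futility followed as about 0.79 or 0.81. The cost is one rerun of the design output and about one percentage point of power. At 284 per arm this falls just below the 0.80 target; about 291 evaluable per arm would restore it (290 gives 0.799, 295 gives 0.806).
- **Binding futility, made explicit.** Keep -1.9308 and state in sections 10.3.7 and 12.7 that the sponsor is committed to stop at any futility crossing, and align section 5.8.4. This changes no limit, sample size or power, but gives up the freedom to continue.

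Under either route, reconcile the look-2 futility limit (-1.1224 in the section 12.5 table, -1.224 in section 12.7).

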12.7 Interim analysis

The group-sequential study design provided two interim analyses when 190 and 378 patients completed the study. Figure 2 shows the stopping limits for the first interim analysis.

[figure not shown]

Figure 2.

Three conditions will be possible:

- Z-statistics in the favorable zone: stop for efficacy ($z \leq -3.710$)
- Z-statistics in the unfavorable zone: stop for futility ($z \geq 0.270$)
- Z-statistics in the promising zone ($-3.710 < z < 0.270$)

For the first interim analysis, only the conditions of futility and efficiency will be verified. A blinded statistical analysis of the study objective will be carried out and provided to the BMDC, which will advise on the continuation of the study.

Figure 3 shows the stopping limits and the conditions for adaptive re-estimation of the sample size for the second interim analysis.

[figure not shown]

Figure 3.

Three conditions will be possible:

- Z-statistics in the favorable zone: stop for efficacy ($z \leq -2.511$)
- Z-statistics in the unfavorable zone: stop for futility ($z \geq -1.224$)
- Z-statistics in the promising zone ($z > -2.511$ and < -1.224)

A blinded statistical analysis of the study objective will be carried out and provided to the IMDC, which will advise on the continuation of the study.

Regarding the possibility of falling into the promising zone and considering clinically valid increase in patients with a favourable outcome compared to the control arm of at least 8 percentage points (NNT@12), two simulations with 100,000 samples were performed.

First, given the sample size (630 patients), the response rate in the control group was from 0.68 to 0.70, and the response rate in the experimental group was fixed at 0.76; the boundary equal to -1.9308 as the O'Brian-Fleming expenditure function for the third interim analysis; solving then for beta (Table 4 shows the simulation plan).

Table 4. Simulation Design for the last look

Scenario	Power	N1	N2	Alpha	Responders control	Responders treatment
1	0.580	315	315	0.025	0.68	0.76
2	0.477	315	315	0.025	0.69	0.76
2	0.379	315	315	0.025	0.70	0.76

The second simulation, with the same sample size and the same boundary, but in this case, varying the response rate in the experimental group (from 0.76 to 0.70) and response rate in the control group fixed at 0.65 (Table 3 shows the simulation plane)

Table 4. Simulation Design for the last look

Scenario	Power	N1	N2	Alpha	Responders control	Responders treatment
1	0.556	315	315	0.025	0.65	0.73
2	0.656	315	315	0.025	0.65	0.74
2	0.753	315	315	0.025	0.65	0.75

Should one of the scenarios occur, a new sample size estimate will be possible. A conditional power analysis for the emerging z-value will be performed and provided to the IDMC.

Independent Data Monitoring Committee (IDMC)

An independent Data Monitoring Committee (IDMC) will closely review the safety data and efficacy of the interim analysis and provide recommendations for the continuation of the study. The IDMC will be composed of at least three members, of which at least one will be a specialist in the domain of neurology and at least one in the domain of reanimation and a methodologist. The members of the IDMC will be appointed before the protocol is submitted to the ethics committee for final approbation.

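### The futility limit for the second interim analysis is -1.1224 in the design output but -1.224, twice, in the stopping rule of Section 12.7; only -1.1224 belongs to the stated design

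*Protocol*

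**What the plan says.** Section 12.5 prints the three-stage design: 95, 189 and 284 patients per arm at the three looks, rates of 0.65 and 0.76, one-sided alpha 0.025, power 0.8016, and O'Brien-Fleming-type spending for both alpha and beta. It declares "Futility Boundaries: Binding". In the table of boundary probabilities, the second look has an efficacy limit of -2.5111 and a futility limit of -1.1224, and the probability of stopping for futility there is 0.0885. Planned cumulative beta at that look is 0.1165. Negative z favours cilostazol.

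Section 12.7 turns this into an operating rule for the second look in three bullets. The bullet on futility reads "Z-statistics in the unfavorable zone: stop for futility ($z \geq -1.224", which is not the value in the design output. The bullet on efficacy uses -2.511, which agrees with the design output at three decimals. The remaining bullet repeats the deviating number as the upper edge of the middle zone: "Z-statistics in the promising zone ($z > -2.511$ and < -1.224".

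For results in that middle zone the section adds: "Should one of the scenarios occur, a new sample size estimate will be possible". The analysis goes to the monitoring committee, "which will advise on the continuation of the study".

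**The concern.** The futility limit at the second look has two values, and nothing in the text gives a reason for the second. The other three interim limits in Section 12.7 (-3.710, 0.270 and -2.511) are the values of Section 12.5 at three decimals (from -3.7103, 0.2701 and -2.5111). On that pattern -1.1224 should appear as -1.122. The figure -1.224 is what remains when one digit of -1.1224 is lost.

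For z from -1.224 up to, but not including, -1.1224, Section 12.7 stops the trial for futility. Section 12.5 continues it, in a zone where the sample size may be re-estimated. If the result falls there, someone must choose the limit after seeing the data, and a stop cannot be undone by a later analysis.

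**Working it through.** **Inputs (Section 12.5).** Rates 0.65 and 0.76; one-sided alpha 0.025; beta 0.20; binding futility; 95, 189 and 284 per arm.

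**Step 1: reproduce the information.** Maximum information = 284 / (0.65 x 0.35 + 0.76 x 0.24) = 284 / 0.4099 = 692.85, as printed. The expected final z, in absolute value, is 0.11 x sqrt(692.85) = 2.895. With pooled variance the information is 284 / (2 x 0.705 x 0.295) = 682.77 and the expected z is 2.874. Section 12.5 does not say which variance was used, so ranges below cover both.

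**Step 2: reproduce the spending.** The function is 2 x [1 - Phi(c / sqrt(t))], where c is the normal quantile that makes it equal the total at t = 1. At t = 1/3 and 2/3:

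- alpha: 0.0001 and 0.0060
- beta: 0.0264 and 0.1165

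All four agree with the printed tables.

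**Step 3: solve the limits.** Recursive numerical integration at information 1/3, 2/3 and 1 gives efficacy limits -3.7103, -2.5111 and -1.9309, and futility limits 0.2700, -1.1225 and -1.9309. All six agree with Section 12.5 to within 0.0001. Placing the looks at 0.33 and 0.67, or at 95/284 and 189/284, moves the second futility limit only to -1.135 or -1.118. No timing variant gives -1.224.

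**Step 4: compare the two limits at 284 per arm.** Integration uses looks at 95, 189 and 284 per arm; simulation uses 2,000,000 binomial trials. Each range runs over pooled and unpooled variance.

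| Quantity | Protocol | With -1.1224 | With -1.224 |
|---|---|---|---|
| Futility stop at look 2, integration | 0.0885 | 0.089-0.092 | 0.108-0.111 |
| Futility stop at look 2, simulation | 0.0885 | 0.087-0.089 | 0.105-0.107 |
| Cumulative futility by look 2, integration | 0.1165 (beta spent) | 0.115-0.118 | 0.134-0.138 |
| Failure at final look, simulation | 0.0821 | 0.083-0.084 | 0.073-0.074 |
| Power, integration | 0.8016 | 0.797-0.803 | 0.787-0.793 |
| Alpha, integration | 0.025 | 0.0250 | 0.0241 |

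The solved limit and the stopping probabilities separate the two values clearly. Power and alpha separate them only weakly.

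**Step 5: size of the strip.** About 1.9% of trials fall between the limits by integration, under the planned effect and under the null alike. With 189 per arm the standard error of the difference is sqrt(2 x 0.705 x 0.295 / 189) = 0.0469, so the limits correspond to observed differences of 1.1224 x 0.0469 = 0.053 and 1.224 x 0.0469 = 0.057.

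**Step 6: what continuing would offer.** Conditional power in the strip, with final limit -1.9308 and 284 per arm:

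- planned effect: 46-53%
- 65% against 73%: 29-34%
- observed trend: 17-23%
- no effect: 4-5%

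**The case against.** The strongest reply is that this is a clerical slip. The full boundary table stands in Section 12.5, so the digit can be traced. The loss is about one point of power, alpha is lowered, and few trials land in the strip. There the observed gain is below the 8 points that Section 12.7 treats as clinically valid, and conditional power under the observed trend is only 17-23%. All of this is true and limits the size of the point. It does not settle which of the two printed limits governs, and Section 12.7 is where the committee would look for the rule.

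Two further objections are fair. Alpha is poor evidence for -1.1224: simulated with unpooled variance, it reaches 0.0255 with -1.1224 and 0.0246 with -1.224, and the printed 0.025 lies between. Nor is a power just under 0.80 peculiar to the error, since pooled variance with the correct limit already gives 0.797. If all 315 per arm were analysed at the end (an assumption), power with -1.224 would be 0.806-0.812.

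On whether futility will be obeyed, the protocol declares it binding, so there is no error of design. A clarification is still useful because the committee advises, "The sponsor retains decision-making authority", and "the precise operating methods of the DSMB will be described in the" charter, which is not at hand. If futility crossings were overruled while -1.9308 was kept, alpha would be 0.0254 (first look only), 0.0277 (second only) or 0.0284 (both).

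**Conclusion.** The concern holds. The futility limit for the second look is stated wrongly, twice, in Section 12.7; the value that follows from the stated design is -1.1224. Applying -1.224 at 284 per arm would raise futility stops at that look by about 2 percentage points under the planned effect, cost 0.9 to 1.0 point of power and bring alpha down to about 0.024. These sizes rest on the rates of 65% and 76%, looks at 95, 189 and 284 per arm, and futility being followed. Correction is needed because a binding stopping limit is contradictory and the two versions lead to different decisions for the same data; the numerical loss alone would not require it. Figure 3 is not visible in the text at hand, so the value drawn there is unknown.

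**What to change.** In Section 12.7, replace -1.224 by -1.1224 (or -1.122, to match the three decimals used there) in both the futility bullet and the promising-zone bullet, and check Figure 3 against it. This changes two figures, needs no redesign, and should be done before the second interim analysis.

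Two optional clarifications:

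- Add one sentence that the sponsor will follow a futility crossing, which keeps the final limit at -1.9308. If the sponsor prefers non-binding futility, the design must be re-run: the final limit becomes about -1.993 at 284 per arm (power about 0.79 with futility followed) or about -2.002 at 315.
- As a separate matter, Section 12.1 describes all tests as two-sided but gives a unilateral level of 0.025%, while Section 12.5 uses one-sided 0.025. Remove the percent sign, state that one-sided 0.025 applies to the primary group-sequential test, and state the sidedness of the other tests.

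### The Table 4 powers in section 12.7 do not match the stated 315 per arm at the last look, and they are not conditional on the promising zone for which they are offered

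*Protocol*

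**What the plan says.** Protocol section 12.5 sets the design: "Therefore set unilateral alpha at 0.025 and the power of the test (1-beta) at 0.80, 284 patients are needed per experimental arm". It then allows for loss: "A drop-out rate of no more than 10% is expected so that the sample size will be 630 patients (315 per experimental arm"). The interim looks are planned on completers, without that allowance: "Only the final analysis will bear any inflationary share of the sample". Futility is binding ("Futility Boundaries: Binding"), and the boundary table gives "1 95 95 -3.7103 0.0253 0.2701 0.0277" for the first look and "2 189 189 -2.5111 0.4166 -1.1224 0.0885" for the second. The final limit is -1.9308.

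Section 12.7 prints the second-look futility limit as -1.224, where the boundary table has -1.1224. It then turns to a trial that falls in the promising zone and reports two simulations of 100,000 samples: "First, given the sample size (630 patients), the response rate in the control group was from 0.68 to 0.70", against 0.76 on treatment, and then control fixed at 0.65 against 0.73, 0.74 and 0.75. Both result tables are numbered 4, are headed as referring to the last look, and list 315 in each arm. The printed powers are 0.580, 0.477, 0.379 and 0.556, 0.656, 0.753. The next step is: "Should one of the scenarios occur, a new sample size estimate will be possible". A conditional power analysis at the emerging z is also promised to the monitoring committee.

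**The concern.** The tables frame the decision whether to enlarge the trial at the second look. A power figure should follow from the sample size, limit and rates printed beside it, and here it does not if the description is taken at face value. The figures are also offered for a trial that has reached the promising zone, but nothing in the description conditions on the second-look result. A committee that takes them as the chance of success from that point could misjudge the need for more patients.

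**Working it through.** **Inputs.** Rates, n = 315 and limit 1.9308 (in favour of cilostazol) from section 12.7. Looks at 95/189/284 per arm, efficacy limits 3.7103/2.5111/1.9308 and futility limits -0.2701/1.1224 in favour from section 12.5. A simulation of that three-look design at 0.65 against 0.76 gives power 0.800, against the protocol's 0.8016, so the design itself reproduces.

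**Step 1: one test at the last look.** Power = Φ(d / √[(p₁q₁ + p₂q₂)/n] − 1.9308). For 0.68 against 0.76, d = 0.08 and p₁q₁ + p₂q₂ = 0.2176 + 0.1824 = 0.4000.

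- n = 284: 0.08/√(0.4000/284) = 2.132; Φ(0.201) = 0.580.
- n = 315: 0.08/√(0.4000/315) = 2.245; Φ(0.314) = 0.623.

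**Step 2: the sequential design.** Simulation with all three looks and binding futility (2,000,000 trials per scenario), ending at 315 or 284.

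| Control / treatment | Printed | Single test, 284 | Single test, 315 | Looks 95/189/315 | Looks 95/189/284 |
|---|---|---|---|---|---|
| 0.68 / 0.76 | 0.580 | 0.580 | 0.623 | 0.570 | 0.546 |
| 0.69 / 0.76 | 0.477 | 0.477 | 0.517 | 0.470 | 0.448 |
| 0.70 / 0.76 | 0.379 | 0.376 | 0.409 | 0.367 | 0.350 |
| 0.65 / 0.73 | 0.556 | 0.555 | 0.598 | 0.544 | 0.520 |
| 0.65 / 0.74 | 0.656 | 0.659 | 0.703 | 0.647 | 0.622 |
| 0.65 / 0.75 | 0.753 | 0.753 | 0.795 | 0.742 | 0.717 |

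With 100,000 samples the simulation standard error is about √(0.58 × 0.42/100,000) = 0.0016. The single test at 284 differs from the printed values by at most 0.003, which is within simulation error. The single test at 315 is higher by 0.030 to 0.047. The planned looks ending at 315 are lower by 0.007 to 0.013, beyond simulation error but close. With a pooled variance the single-test values fall by up to about 0.003, which changes nothing here.

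**Step 3: power given the promising zone.** Average power among simulated trials with a second-look z between 1.1224 and 2.5111 in favour:

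| Control / treatment | Printed | Final n 315 | Final n 284 |
|---|---|---|---|
| 0.68 / 0.76 | 0.580 | 0.698 | 0.650 |
| 0.69 / 0.76 | 0.477 | 0.631 | 0.585 |
| 0.70 / 0.76 | 0.379 | 0.556 | 0.518 |
| 0.65 / 0.73 | 0.556 | 0.686 | 0.637 |
| 0.65 / 0.74 | 0.656 | 0.751 | 0.701 |
| 0.65 / 0.75 | 0.753 | 0.811 | 0.761 |

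The printed values are 6 to 18 points below the average at 315 and 1 to 14 points below it at 284.

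**Step 4: within the zone.** Conditional power = Φ([z√t + θ(1 − t) − 1.9308]/√(1 − t)), with t = 189/n and θ the drift at the final look. For 0.68 against 0.76 at n = 315, t = 0.6 and θ = 2.245:

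- z = 1.1224: (0.869 + 0.898 − 1.931)/0.632 = −0.26, power 0.40.
- z = 1.8: power 0.72.
- z = 2.511: power 0.93.

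The printed 0.580 is too high at the futility edge and too low over the upper part of the zone.

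**The case against.** The tempting stronger reading is that the tables are simply mislabelled: 315 is printed where 284 was used. The documents do not establish this. Section 12.7 does not say whether the simulation was one final test or the whole sequential design. Under the trial's own three-look design the printed values lie within about 1 point at 315 and miss by about 3 to 4 points at 284. Looks at 105/210/315 with the -1.224 limit come closer still, with a largest gap of 0.0075. That variant departs from the protocol's 95 and 189 per arm and from the boundary table's futility limit, but it shows that a sequential source at 315 cannot be excluded. Further, 315 × 0.9 = 283.5, so a 284-based figure beside 315 may mean evaluable beside randomised patients. A reader might also infer that the planned 630 already has more power than printed. That holds for the last-look test only if all 315 per arm are evaluable, which is not the protocol's own loss assumption.

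A second tempting reading is that the tables understate power throughout the promising zone. They do so on average, but not near the futility edge.

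Finally, the committee is to receive conditional power at the observed z, which is more specific than any scenario table. This limits the harm; it does not make the printed figures agree with their description.

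**Conclusion.** The point holds in this form. On the terms printed beside them, the Table 4 powers are 3 to 5 points too low. None of the calculations tried that keeps to the stated n, look sizes and limits reproduces them within simulation error; the nearest, the planned looks ending at 315, is about 1 point lower. Their source cannot be settled from the text. Separately, and whichever source applies, they do not describe a trial in the promising zone: average power there is higher in all six scenarios, while conditional power near the futility edge is lower than printed. These results assume independent binomial outcomes, an unadjusted z-test, the second-look limit of -1.1224 unless stated, and either full evaluability (315) or about 10% loss (284). It is worth correcting before the second look. It does not affect the main sample size or the final limit.

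**What to change.** State in section 12.7 which calculation produced the tables: the looks, the limits, and whether n counts randomised or evaluable patients. Reconcile the second-look futility limit (-1.1224 in section 12.5, -1.224 in section 12.7). Then correct the N label, or recompute the powers to match it. Relabel as 284 per arm, single look, only if the sponsor confirms that this was what was run. Add power conditional on the second-look promising zone, preferably tabulated by z across the zone, to stand beside the planned conditional power analysis. The cost is one rerun of the simulation, two corrected tables and a sentence of description.
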